**Protocol Test Abstract:**

This study is designed to evaluate the trending accuracy of a noninvasive regional oximetry measurement of somatic oxygen saturation. One investigational sensor (INVSENSOR00038) will be placed on the somatic site of the volunteer. The values obtained by the test sensor will be compared to the reference value obtained from an FDA-cleared sensor placed on the somatic site on the contralateral side.

Data will be collected from healthy adult subjects while undergoing a desaturation procedure wherein the concentration of oxygen inhaled is slowly reduced [REDACTED] The subject will then be returned to inhaling room air.

## Desaturation Validation of INVSENSOR00038

## STATEMENT OF COMPLIANCE

This document is a protocol for a clinical research study sponsored by Masimo Corporation. The study will be conducted in compliance with all stipulations of this protocol, the conditions of IRB approval and applicable regulations including 21 CFR Part 50, 21 CFR Part 56, 21 CFR Part 812, ISO-14155, and International Conference on Harmonisation E6 Good Clinical Practice (ICH GCP).

The protocol, informed consent form(s), recruitment materials, and all participant materials will be submitted to the Institutional Review Board (IRB) for review and approval. Approval of both the protocol and the consent form must be obtained before any participant is enrolled. Any amendment to the protocol will require review and approval by the IRB before the changes are implemented to the study.

**1. PURPOSE**

This study is designed to evaluate the trending accuracy of O3 system's measurement of oxygen saturation in somatic sites.

The INVSENSOR00038 is Masimo's O3 system, which has been cleared by the FDA for rSO2 measurements in the cerebral tissue. The INVSENSOR00038

and is considered an investigational device when placed over skeletal muscle. The values obtained by the INVSENSOR00038 will be compared to reference values.

This is a nonrandomized study wherein all subjects receive both the somatic sensor (INVSENSOR00038) and one FDA-cleared device sensor. Data using the sensors will be collected from healthy volunteers undergoing a desaturation procedure. Desaturation will be conducted by reducing the concentration of oxygen the study subject breathes in a controlled manner to obtain noninvasive regional oxygen saturation readings, rSO2, at various levels.

**Outcome Measure:**

This study will evaluate the trending accuracy of the INVSENSOR00038 relative to the reference value obtained from the comparative FDA-cleared device.

**2. BACKGROUND**

Masimo Corporation develops non-invasive medical technologies. These devices have applications in the operating room, critical care unit, emergency room, emergency transport vehicles, as well as physician's offices.

**2.1. Technology Background**

Regional oximetry is a noninvasive technology for measuring the level of oxygenation in deep tissue (rSO2). To arrive at their measurements, regional oximeters use Near Infrared Spectroscopy (NIRS), which is based on the Beer Lambert Law.

For cerebral oximetry, multiple detectors and emitters are utilized to provide multiple pathways for the light to travel through the tissue. Software algorithms then process the received light signals to provide an oxygenation measurement.

## Desaturation Validation of INVSENSOR00038

In addition to assessing brain oxygenation, the O3 system can be used to for oxygenation measurement in somatic sites. The oxygenation of somatic tissue can be used clinically in applicable medical, surgical, and trauma patients.

## 2.2. Study Devices

### Investigational sensors: INVSENSOR00038

The INVSENSOR00038 is a system which includes Masimo's O3 neonatal sensor and Masimo's O3 module.

[REDACTED] This sensor will be used in conjunction with the Masimo O3 module that is currently cleared for clinical use on adult and pediatric cerebral tissue in the US and EU countries. The O3 module will be used with the Root monitor that will be used to collect data from the new application site during this study.

### FDA Cleared Sensors and Devices:

Masimo Root Patient Monitoring Platform: Root is a patient monitoring and connectivity platform that offers rainbow® and Masimo SET® measurements with other parameters in an integrated platform. With docking capabilities for the Radical-7® handheld monitor and multiple networking/connectivity options, Root integrates multiple streams of data into one display monitor.

### FDA Cleared Comparator Device

The FDA cleared comparator device provides real-time monitoring of changes in regional oxygen saturation (rSO2) of blood in the brain or other body tissues beneath the sensor. The system utilizes near-infrared light at wavelengths that are absorbed by hemoglobin. Light travels from the sensor's light emitting diode to a proximal and a distal detector, permitting data processing of the optical signals.

The output measurement is a real-time rSO2.

## 5. STUDY POPULATION

## 5.1. Inclusion Criteria

- Subject is between 18 and 50 years of age.
- Subject weighs a minimum of 110 lbs and no more than 250 lbs unless subject is over 6 feet tall.
- Must have a hemoglobin value greater than or equal to 11 g/dL.
- Baseline heart rate  $\geq$  45 bpm and  $\leq$  85 bpm.
- Blood Pressure (Systolic BP  $\leq$  140 mmHg and Diastolic BP  $\leq$  90 mmHg).
- CO value  $\leq$  2.0% FCOHb
- Subject has a physical status of ASA I or II (American Society of Anesthesiology Class I; Healthy subjects without any systemic disease at all. American Society of Anesthesiology Class II; subjects with mild systemic disease) as it applies to the systemic disease portion of the classification.
- Subject is able to read and communicate in English and understands the study and risks involved.

## Desaturation Validation of INVSENSOR00038

5.2. **Exclusion Criteria (\*= Per physician discretion)**

- Subject is pregnant.
- Subject smokes (including e-cigarette use).
- Subject has a BMI > 35 and has been classified as morbidly obese or at an increased risk for participation by a medical professional.
- Subject has a history of fainting (vasovagal), blacking out or losing consciousness during or after a blood draw, or has a fear of blood draws.
- Subject has open wounds, inflamed tattoos or piercings and/or visible healing wounds that a medical professional renders them at an increased risk for participation.\*
- Subject experiences frequent or severe headaches and/or migraine headaches, migraine auras, altitude sickness, and/or headaches accompanied by visual changes or sensitivity to light or sound.
- Subject has known drug or alcohol abuse and/or uses recreational drugs.
- Subject has experienced a concussion or head injury with loss of consciousness within the last year.
- Subject has any chronic bleeding disorders (i.e. hemophilia).
- Subject has any history of a stroke, myocardial infarction, seizures or heart attack.
- Subject has any cancer or history of cancer (not including skin cancer)\*.
- Subject has a known neurological and/or psychiatric disorder (i.e. schizophrenia, bipolar disorder, Multiple Sclerosis, Huntington's disease) that interferes with the subjects' level of consciousness.
- Subject has any cardiac dysrhythmia(s) (i.e. atrial fibrillation) and has not received clearance by their physician to participate.
- Subject has Wolff-Parkinson-White Syndrome or Stokes-Adams Syndrome.
- Subject has taken anticoagulant medication within the last 30 days (excluding nonsteroidal anti-inflammatory drugs (NSAIDS)).
- Subject has donated blood within the past 4 weeks.
- Subject has taken opioid pain medication within 24 hours before the study.
- Subject has any type of infectious disease (i.e. Hepatitis, HIV, Tuberculosis, Flu, Malaria, Measles, etc.).
- Subject is taking medications known to treat any type of infectious disease.
- Subject has either signs or history of peripheral ischemia or carpal tunnel syndrome.
- Subject has had invasive surgery within the past year- including but not limited to major dental surgery\*, appendix\*, plastic surgery\*.
- Subject has had invasive surgery within the past year- including but not limited gallbladder, major fracture repairs (involving plates/ screws), jaw surgery, urinary tract surgery, major ENT surgery, joint replacement or gynecological surgeries, heart surgery or thoracic surgery.
- Subject has symptoms of congestion, head colds, flu or other illnesses.
- Subject is claustrophobic and/or has generalized anxiety disorder.
- Subject has been in severe car accident(s) or a similar type of accident(s) requiring hospitalization within the last 12 months.
- Subject has chronic unresolved asthma, lung disease or respiratory disease.
- Subject is allergic to lidocaine, latex, adhesives, or plastic.
- Subject has a heart condition, insulin-dependent diabetes or uncontrolled hypertension.
- Subject has delivered vaginally, has had a pregnancy terminated, a miscarriage with hospitalization or had a C-section within the last 6 months.
- Subject has any medical condition which in the judgment of the investigator and/or medical staff, renders them ineligible for participation in this study (Discretion of investigator/study staff).

## Desaturation Validation of INVSENSOR00038

**5.3. Withdrawal of subjects**

Subjects must be withdrawn under the following circumstances:

5.3.1 The subject withdraws consent.

5.3.2 Discretion of investigator, for example:

- The investigator feels that the subject is too money motivated.
- The investigator feels that the subject does not fully comprehend and understand the consent form.
- The subject is ill-mannered and/or shows aggressive behavior towards study staff.
- Malfunction of the device for greater than 30 minutes that prevents accurate collection of optical data.
- Subject displays or communicates signs of discomfort or distress so that the study may not be continued.

**5.4. Replacement of subjects**

In case a subject is withdrawn from the study, another subject may be recruited.

**6. EQUIPMENT AND MATERIALS**

Equipment and Materials: All lab analyzers and equipment will be maintained per manufacturer specifications and all study personnel will be trained on the use of relevant equipment. Equivalent equipment and materials to those listed below may be used.

Safety Equipment (FDA-Cleared)

- Blood pressure monitoring system
- Electrocardiogram (ECG)
- Masimo Pulse Oximeters (Radical-7)
- Masimo Patient Monitoring Platform (Root®)
- Pulse oximeter sensors and cables (Masimo SET, Masimo rainbow, or comparable)
- Medical-grade oxygen tank and mask
- Crash cart

Test Devices

- Masimo INVSENSOR00038

Reference Device

- Tissue oximetry system FDA-cleared for somatic use

Research Equipment

[figure not shown]
- Masimo Patient Monitoring Platform (Root®)
- O3 Regional Oximeter Module

Passive Data Collection Research Equipment

## Desaturation Validation of INVSENSOR00038

## 7. PROCEDURE

## 7.1 SCHEDULE OF ACTIVITIES

## 7.2. RECRUITMENT AND PRESCREENING

Subjects will be recruited using IRB-approved advertisements. Subjects may be referred to the study by previous subjects. Subjects are contacted via phone call to conduct a prescreening interview to determine their initial eligibility for the study. Potential eligible subjects are scheduled for a study visit to the clinical laboratory.

## 7.3. CONSENTING AND SCREENING

- 7.3.1. Study staff will discuss the informed consent process and the study with the potential subjects. The subjects will be provided with enough time to read and understand the informed consent document and their questions will be answered by study staff prior to the subject signing the informed consent form. No study related activities will be conducted until consent is signed. If the subject fails to provide proper documentation on their individual consent form for any study, Masimo has the right to re-contact the subject and ask them to return to the clinical lab in order to properly complete the consent form or subject bill of rights.
- 7.3.2. The subject's weight and height are self-reported, however the subject may be weighed on a scale for verification.

## Desaturation Validation of INVSENSOR00038

- 7.3.3. Subjects will be asked to provide a copy of their valid government photo ID and/or Social Security Number (SSN) card to verify subject identity. The copies of these forms of identification will be stored along with the subject's consent. The confidentiality and retention of these documents will be protected to the extent provided and required by law.
- 7.3.4. Subjects will be asked a brief series of health questions to ensure their eligibility for this study. Subjects must meet all the inclusion criteria and none of the exclusion criteria in order to participate in the study.
- 7.3.5. Subject demographic information including age, sex, skin tone, ethnicity, height and weight will be collected. These may be recorded for data analysis purposes.
- 7.3.6. In addition, a medical history will be recorded after the initial screening questionnaire.
- 7.3.7. Pre-procedure vital signs will be recorded for subject safety monitoring. Spikes in blood pressure and heart rate can be expected during line placement, needle sticks, blood draws etc. and may also be attributed to anxiety/nervousness relating to a new environment. Only the initial recorded blood pressure and/or heart rate determines a subject's qualification for the study.
- 7.3.8. Female subjects will be required to take a pregnancy test. Results will be noted in study documentation. If the pregnancy test is positive, the subject will be notified and removed from the study.
- 7.3.9. A venous sample will be obtained via needle stick or by placement of an IV and analyzed to verify that the subject meets the inclusion criteria for hemoglobin level and FCOHb. The subject will be excluded from the study if the values from the blood draw fall outside the ranges stated in the inclusion criteria.

7.3.11. Subjects may be offered a snack (e.g., granola bar) and/or beverage (e.g., water, juice) due to the amount of time their involvement in this study may take.

#### 7.4. PROCEDURES

- 7.4.1. Standard hospital-type monitors will be placed on the subject, including ECG, blood pressure, and a reference pulse oximeter for safety monitoring by medical staff.
- 7.4.2. Proprietary Masimo data collection software will be used to verify all oximeters are reading. If not, proper sensor positioning will be checked and sensors may be repositioned, as needed.
  - 7.4.2.1 Pulse oximeter output values (e.g., SpO2, Pulse rate) will be recorded using the proprietary Masimo data collection software. These values match the values calculated by the instrument at runtime.
  - 7.4.2.2 Raw absorbance data from the noninvasive device(s) will also be recorded using the data collection software.
- 7.4.3. A peripheral venous line(s) will be placed in the subject's arm. One or more venous sampling catheters may be placed and used for the qualifying venous blood draw and/or for safety or clinical intervention required during the study.

## Desaturation Validation of INVSENSOR00038

7.4.4 Local anesthetics such as lidocaine, ethyl chloride spray, or Pain Ease skin refrigerant spray may be used in the event that an IV is placed to numb the site. Subjects will be given the option to have lidocaine or numbing spray be used during IV placement for the purpose of making catheter placement more comfortable for the subjects.

7.4.5 Sensor of the control device will be placed on one side of the somatic site and INVSENSOR00038 will be placed on the other side of the somatic site. Subjects may be asked to shave the area prior to sensor placement. If the subject declines to shave they may be kept from participating in the study.

Upon indication the subject is comfortable, a gas mixture will be administered. The proportion of oxygen in this mixture will be decreased in a controlled manner to lower the subject's blood oxygen saturation. The lowest targeted value will be [REDACTED] oxygen saturation as measured by [REDACTED]. Note: At any point in the study, if the subject feels uncomfortable, the subject will be given 100% oxygen [REDACTED]

7.4.14 The study will end with several minutes at a FiO2 greater than room air (>21%) to help the subject re-saturate after the procedures.

7.4.16 At the conclusion of the procedure, the sensors/devices, and IV(s) will be removed and the subject will be allowed to leave after medical personnel determine it is safe to do so.

7.4.17 Study staff may take one final blood draw 1-4cc to verify the subjects blood values are within normal range (eg. pH, Glucose, etc.). These values will be assessed by a physician and the subject will then be cleared to leave the study space.

7.4.18 The total procedure time will be approximately [REDACTED]

7.4.19 All subjects will be encouraged to remain in the study area until they feel fit to leave.

7.4.20 Subjects will be given instructions on wound care. All subjects will be instructed to contact the principal investigator or study staff in the event of any potential complication.

7.4.21 Subjects will be paid for their time.

7.4.22 Subjects will be provided with information related to any significant new findings that develop at any time during the study which may relate to their willingness to continue their participation.

7.4.23 After the study has ended subjects will be offered a snack (eg. Granola bar) and something to drink (eg. water or juice). Subjects are asked to consume food and/or liquid prior to leaving the clinical lab area for their safety. Subjects may also be asked to wait in the clinical lab or lobby waiting area for an additional 30 minutes (estimate) before leaving to allow for their body to continue adjusting after the study has completed.

## 7.5. RE-CONTACTING SUBJECTS

If the subject fails to provide proper documentation on their individual consent form for any study, Masimo has the right to re-contact the subject and ask them to return to the clinical lab in order to properly complete the consent form or subject bill of rights. Subject will be compensated for travel.

## Desaturation Validation of INVSENSOR00038

Other than the IRB approved consent form, the subject will also fill out Masimo study documents. Masimo study documents aid in the collection of data, tracking subject count, etc. and do not affect subject safety or the consenting process. If the subject fails to provide proper documentation on Masimo documents the subject will not need to return to the laboratory in order to complete these specific forms.

The subject will be re-contacted via phone or email and be asked to return within 1 week from their last appointment or from the point in which the missing documentation was identified.

## 8. ACCEPTANCE CRITERIA (JUSTIFY IF NOT APPLICABLE)

[REDACTED]

## 9. SAMPLE SIZE JUSTIFICATION AND DATA ANALYSIS PROCEDURE TO BE USED

## 9.1. Sample size determination

[REDACTED]

[REDACTED]

[REDACTED]

[REDACTED]

[REDACTED]

[REDACTED]

[REDACTED]

[REDACTED]

## 9.2. Statistical Analysis

INVSENSOR00038 is placed on the somatic site. Reference sensor from the control device is placed on the somatic site on the contralateral side.

## 9.2.1. Exclusion criteria for data analysis

The following exclusion criteria will be applied before data analysis.

- i. Either reference or test device do not provide data.

## Desaturation Validation of INVSENSOR00038

- ii. Incomplete study or early termination where desaturation protocol could not be completed.
- iii. Reference device malfunctions, provides inconsistent saturation values.
- iv. Discontinuities and abrupt dropouts due to instruments recalibration or device failure.
- v. Low signal quality (e.g. due to noise or interference).

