#### 9.2.2. Relative error and trend accuracy calculations

In order to compute error, discrete time points along the continuous trances will be selected in a consistent fashion. The data points will be selected with a minimum of 5 min interval.

Relative error in rSO2 is computed on a sensor by sensor (i.e. subject by subject) basis.

Relative error is defined to be the relative difference of the test sensor and reference sensor rSO2.

Trending Accuracy is defined as root-mean-squared relative error of discrete data points across subjects.

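### Exclusion rule iii does not say what the reference values must be inconsistent with, so its wording permits, without requiring, exclusions driven by test-reference disagreement

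*Combined protocol and SAP*

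**What the plan says.** The outcome in section 1 (Outcome Measure) is the "trending accuracy of the INVSENSOR00038 relative to the reference value obtained from the comparative FDA-cleared device". Section 1 also states that "all subjects receive both the somatic sensor (INVSENSOR00038) and one FDA-cleared device sensor". Section 9.2 puts the two sensors on opposite sides: "Reference sensor from the control device is placed on the somatic site on the contralateral side". Section 6 lists a single tissue oximetry system as the reference device.

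Section 9.2.2 builds the endpoint in two steps: "Relative error is defined to be the relative difference of the test sensor and reference sensor rSO2", and then "Trending Accuracy is defined as root-mean-squared relative error of discrete data points across subjects".

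Section 9.2.1 comes first in the workflow: "The following exclusion criteria will be applied before data analysis". Of its five rules, the third covers the case "Reference device malfunctions, provides inconsistent saturation values". In the visible text this rule has no numeric limit, no time window and no named comparator. It does not say who decides, or whether that person can see the test trace. The other four rules cover missing data from either device (i), an incomplete desaturation (ii), discontinuities and dropouts (iv), and low signal quality (v).

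Pulse-oximeter SpO2 is also captured under section 7.4.2.1 ("Pulse oximeter output values (e.g., SpO 2 , Pulse rate) will be recorded using the proprietary Masimo data collection software"), but no visible text links it to rule iii. Section 9.3, on bias, shows only its heading.

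**The concern.** Rules i, iv and v already deal with a reference that is silent, drops out or has a poor signal. What the second half of rule iii mainly adds is reference values that are present, continuous and of acceptable signal quality, yet judged to be wrong. That judgement needs something to compare with, and the rule names nothing. The only other rSO2 trace described is that of the device under test.

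If a reviewer used that trace, a stretch where the two devices part could be put down to the reference and removed. Exclusion would then depend on the quantity that defines the endpoint. A test sensor with a clean signal and a wrong value could have some of its worst errors taken out. The RMS gives most weight to the largest differences, so it is sensitive to exactly this kind of selection.

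**Working it through.** **No figure to reproduce.** The acceptance criteria (section 8) and sample size (section 9.1) are redacted, and the plan gives no expected error or exclusion rate. The check therefore covers direction first, then an illustrative size.

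**Direction.** Let M be the mean squared relative error over all pairs. Removing pairs whose squared error is above M leaves a mean square below M. Discarding the largest disagreements therefore always lowers the RMS, whatever the error distribution.

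**Illustrative size.** Assumptions, none taken from the documents: relative errors are normal with mean zero, and every pair beyond ±c SD is dropped. With φ and Φ the standard normal density and distribution function:

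RMS kept / RMS full = √[1 − 2cφ(c) / (2Φ(c) − 1)]

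- c = 2.5: φ = 0.01753 and 2Φ − 1 = 0.98758. The ratio is √(1 − 5 × 0.01753 / 0.98758) = √0.9113 = 0.955. So 1.2% of points are removed and the RMS falls by 4.5%.
- c = 2: φ = 0.05399 and 2Φ − 1 = 0.95450. The ratio is √(1 − 4 × 0.05399 / 0.95450) = √0.7737 = 0.880. So 4.6% of points are removed and the RMS falls by 12.0%.

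**Sensitivity to the assumed distribution** (simulation, 2 million points, all inputs assumed):

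- Bias 3 and SD 5 (percent), with the largest 5% of absolute errors dropped: RMS goes from 5.84 to 5.12, a fall of about 12%.
- Heavy tails (90% of points with SD 4, 10% with SD 12), dropping absolute errors above 15: 2.1% of points go and RMS falls from 5.37 to 4.43, about 18%.

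The normal figures are therefore not an upper limit.

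**Zero case.** If inconsistency is judged without the test trace, for instance from the reference monitor's own status, exclusion does not select on the test-reference difference and this bias is absent.

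**The case against.** The strongest reply is that rule iii speaks only of the reference device. Where the authors meant both devices, as in rule i, they named both. The most natural reading may be a reference that behaves erratically in its own trace. Inconsistency can also be judged against the recorded SpO2 or the controlled fall in inspired oxygen, so having only two rSO2 signals does not force a comparison with the test sensor. The exclusions precede the error calculation. Removing true reference faults is also sound, because such faults would otherwise be charged to the test sensor. Finally, the body of section 9.3 is not visible, and blinded review or adjudication could well be described there.

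Most of this stands. It rules out two stronger conclusions that a reader might infer. One is that the plan removes pairs because they disagree; the text permits that but does not require it. The other is that the plan has no blinding or adjudication; with section 9.3 unseen, that cannot be asserted.

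It does not close the point. Applying a rule before analysis does not hide the test trace from the person applying it. The availability of independent comparators also does not help while the rule names none of them.

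**Conclusion.** The concern holds as a gap in the visible wording. Rule iii is a discretionary exclusion with no stated comparator, in a design where the endpoint is the RMS difference between the only two rSO2 traces described. Any use of it driven by disagreement would make the test sensor look more accurate.

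The effect in this trial cannot be computed. It starts at zero, and the 4.5% and 12% figures rest on assumed zero-mean normal errors and sharp cut-offs at 2.5 and 2 SD. A reader might go further and conclude that the outcome can no longer be taken as agreement with the reference. That would follow only if exclusions were in fact driven by disagreement, and nothing in the documents shows this. The point is conditional on section 9.3: if a safeguard is written there, rule iii needs only to refer to it.

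**What to change.** Unless section 9.3 already provides for it, restate rule iii so that a reference value is rejected only on evidence independent of the test sensor:

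- the reference monitor's own fault or signal status;
- erratic behaviour within the reference trace itself; or
- a reference course that contradicts the recorded SpO2 course.

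Existing staff should make the decision without the test trace displayed. Report the number of points removed under rule iii, and trending accuracy with and without those exclusions. State beside the figure without exclusions that it includes any true reference faults. It may be less favourable for that reason, and a gap between the two figures is not by itself evidence of misuse.

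The cost is one reworded rule, a small change in how traces are displayed when exclusions are decided, and one extra run of the same calculation. SpO2 is already recorded, so subjects undergo no added procedure.

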#### 9.3. Measures taken to minimize/avoid bias:

#### 9.4. Expected drop out rates

Subjects may not complete the study for various reasons, such as a clinical screening test failure, unable to complete desaturation

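### Exclusion item v (low signal quality) is not limited to the reference device, so poor readings from the test sensor can be removed before its own RMS error is computed

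*Combined protocol and SAP*

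**What the plan says.** Section 9.2.1 opens with "The following exclusion criteria will be applied before data analysis" and lists five items. Those that bear on this point are:

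- Item i: "Either reference or test device do not provide data". It names both devices and concerns absent data.
- Item iii: "Reference device malfunctions, provides inconsistent saturation values". It names the reference device only.
- Item iv: "Discontinuities and abrupt dropouts due to instruments recalibration or device failure". It names no device but ties exclusion to stated events.
- Item v: "Low signal quality (e.g. due to noise or interference". It names no device. It gives two example causes, but no measure, cut-off or assessor.

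The list does not say whether an exclusion removes single points or a subject's whole trace.

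Section 9.2.2 then says that "discrete time points along the continuous trances will be selected in a consistent fashion", at least 5 minutes apart. It takes the relative difference between test and reference rSO2 as the error, and states: "Trending Accuracy is defined as root-mean-squared relative error of discrete data points across subjects". Trending accuracy is the only outcome named in section 1.

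Section 9.3 is headed "Measures taken to minimize/avoid bias". Its body is not visible in the public text.

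**The concern.** The study evaluates the test sensor. An exclusion that rests on a fault of the reference removes pairs in which the yardstick failed, and that is legitimate. An exclusion that rests on poor signal at the test sensor removes part of the performance being measured. Because the outcome is an RMS, a few large errors weigh heavily in it. If noise or interference at the test sensor tends to go with larger error, removing those points gives a figure better than the error in the values that the device actually output.

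A smaller matter concerns item iii. Inconsistent reference values most naturally means a malfunction visible in the reference trace itself, and on that reading it adds no bias. The wording does not exclude judging inconsistency against the test reading, which would remove pairs because they disagree.

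**Working it through.** **What item v adds.** Item i removes points where either device gave nothing. Applied to points, item v therefore adds points where both devices gave a value. The list names a device in items i and iii and does not in item v, so as written item v covers the test sensor as well as the reference. Consistent selection of time points under section 9.2.2 limits ad hoc choice among the data that remain. It does not limit what item v removes beforehand.

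**No planned figure to reproduce.** The acceptance criteria (section 8) and sample size (section 9.1) are redacted, and the readable text gives no error SD or expected exclusion rate. All inputs below are assumptions.

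**Illustration.** Let a share s of points be low-signal test points whose errors have k times the SD of the rest. Errors are centred on zero and the RMS of the rest is 1.

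- RMS with all pairs = sqrt(1 − s + s·k²)
- RMS after item v removes the low-signal points = 1
- Relative change from removal = 1/sqrt(1 − s + s·k²) − 1

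| k | All-pairs RMS, s = 5% | Change on removal | All-pairs RMS, s = 10% | Change on removal |
|---|---|---|---|---|
| 0.5 | sqrt(0.9625) = 0.981 | +1.9% | sqrt(0.925) = 0.962 | +4.0% |
| 1 | 1.000 | 0% | 1.000 | 0% |
| 1.5 | sqrt(1.0625) = 1.031 | −3.0% | sqrt(1.125) = 1.061 | −5.7% |
| 2 | sqrt(1.15) = 1.072 | −6.7% | sqrt(1.30) = 1.140 | −12.3% |
| 3 | sqrt(1.40) = 1.183 | −15.5% | sqrt(1.80) = 1.342 | −25.5% |

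The share needed to lower RMS by 5% is s = (1/0.95² − 1)/(k² − 1) = 0.108/(k² − 1). That is 8.6%, 3.6% and 1.4% for k = 1.5, 2 and 3.

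**Check by another route.** In a simulation of 2,000,000 normal errors, 10% of points were dropped on a quality score whose correlation with the rank of absolute error (on a normal scale) was 0, 0.3, 0.6 or 1. The RMS after dropping, relative to all points, was 0.999, 0.957, 0.900 and 0.788. The effect is absent when exclusion ignores error size and grows as the two become linked.

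**Unit of exclusion.** Assume 20 subjects with 10 points each, and 10 poor points (k = 1.5) lying in 2 subjects. The result depends on the other 10 points of those 2 subjects; the remaining 180 points have RMS 1.

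- Other points at RMS 1.5: all pairs sqrt((180 + 22.5 + 22.5)/200) = 1.061. Dropping points gives sqrt(202.5/190) = 1.032 (−2.7%); dropping traces gives 1.000 (−5.7%).
- Other points at RMS 0.5: all pairs sqrt((180 + 22.5 + 2.5)/200) = 1.012. Dropping points gives sqrt(182.5/190) = 0.980 (−3.2%); dropping traces gives 1.000 (−1.2%).

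So the unit matters once errors differ between subjects.

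**The case against.** **Unseen text may answer it.** Section 9.3 could hold a signal-quality criterion, a device limit or masked assessment, and text not shown is not missing from the plan. This stands as a limit. A reader might infer from the bare heading that the plan has no protection against bias; the documents do not support that. Masking alone would not change which device's data item v covers, but a device limit or criterion there could.

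**The test device may not output poor values.** The readable text does not say whether it gives an rSO2 value when signal quality is low. If it blanks such values, item i covers them and the test-side change has no effect. This also stands. A reader might look to section 7.4.2.1 for evidence of recorded run-time values, but that item concerns pulse-oximeter outputs, not rSO2.

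**The direction is assumed.** A reader might infer that item v must flatter the sensor. Nothing in the documents links signal quality to error size, and the k = 0.5 row shows the reverse. Larger error under noise is plausible, but it remains an assumption.

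**Item iv also names no device, and item v does give causes.** True. The difference is one of degree: item iv is tied to recalibration or failure, whereas item v's causes are only examples.

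**Every number is illustrative.** Also true, and it limits what can be claimed. It does not remove the textual point that a visible rule reaches the device under test and acts on the study's only outcome.

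**Conclusion.** The point holds in conditional form. As written, item v permits removal of test-sensor values that were output but were of poor quality, before that sensor's RMS relative error is calculated. The reported trending accuracy is too favourable if those points have larger errors than the rest, unaffected if exclusion is unrelated to error size, and too unfavourable if they have smaller errors. Neither size nor direction can be derived from the documents. At an assumed 5% share, the change runs from 1.9% higher (k = 0.5), through none (k = 1), to 15.5% lower (k = 3). It also depends on the unit of exclusion, which the list leaves open.

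A reader might go further and infer that the sensor could pass wrongly. With the acceptance criteria redacted, the documents do not support any statement about the study's conclusion. Removal of true reference faults is not in question. The rule is worth tightening because it bears on the only outcome and the change is cheap. Confidence is moderate, given the unseen body of section 9.3 and the unknown output behaviour of the test device.

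**What to change.** Amend section 9.2.1 as follows.

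1. In the main analysis, exclude a test-sensor point only when the test device output no value or, if such a flag is recorded, when its own pre-specified run-time low-quality flag was set. If no flag is recorded, only the first ground applies.
2. Judge reference exclusions under items iii to v from the reference device's own output, without use of the test reading or the paired difference. If section 9.3 already says this, refer to it.
3. Report excluded points and subjects by rule and by device.
4. Add one sensitivity RMS that restores every test-sensor value excluded for signal quality, including flagged values, and keeps true reference faults excluded. Restoring reference faults as well would mix the two sources of error and would not isolate the effect of test-side exclusions.

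The cost is SAP wording, one table of counts and one further RMS on paired values that the analysis needs anyway. No new subjects or procedures are needed. The downside is a little more analysis work and a reported error that may be somewhat larger.
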